## 9. General arrangements for analysis

### 9.1. Handling of missing data

When analysis is conducted, missing data at that time is not complemented. However, entry data compliment may be conducted in some items, and therefore, data complement method is defined in items in Chapter 10 or later chapters if any entry data complement is needed.

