### 9.2. Descriptive statistics

Following values should be calculated for categorical data and quantitative data

Types of data	Data required to be calculated
Categorical data	
The number or rate of patients
 
When rate of patients is calculated, patients with “unknown” and “not described” data should be included in denominator.
 
In addition, breakdown of patients is displayed as rate, the number of

Types of data	Data required to be calculated
	patients including those with “unknown” and “not described” data from high-order items should be used as denominator. When test is performed, patients with “unknown” or “not described” data should be excluded.
Quantitative data	The number of patients, mean value, standard deviation, median value, the minimum value, and the maximum value should be applicable

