## 11. Method of dividing hierarchy of data

data	Method of dividing hierarchy
Dosage and administration	160mg→80mg→40mg/2 weeks, no changes thereafter 160mg→80mg→40mg/2 weeks, and 160mg or 80mg is administered at least once thereafter 160mg, and not administered thereafter 160mg→80mg, and not administered thereafter 80mg, and not administered thereafter 40mg, and not administered thereafter others
the number of administrations	at least once and less than 4 times at least 4 times and less than 12 times at least 12 times and less than 26 times at least 26 times and less than 39 times at least 39 times and less than 52 times at least 52 times and less than 65 times at least 65 times and less than 78 times at least 78 times
Total dose	lower than 500mg at least 500mg and lower than 1000mg at least 1000mg and lower than 2000mg, at least 2000mg and lower than 3000mg at least 3000mg unknown
Mean daily dose	lower than 40 mg at least 40 mg and lower than 60 mg at least 60 mg and lower than 80 mg at least 80 mg and lower than 100 mg at least 100 mg unknown

data	Method of dividing hierarchy
Administration duration	at least 0 week and shorter than 4 weeks (1-28 days) at least 4 week and shorter than 12 weeks (29-84 days) at least 12 weeks and shorter than 24 weeks (85-168 days) at least 24 weeks and shorter than 52 weeks (169-364 days) at least 52 weeks and shorter than 104 weeks (365-728 days) at least 104 week and shorter than 156 weeks (729-1093 days) unknown * When the start date of the administration is defined as 1
Reasons for discontinuation	Occurrence of adverse events, insufficient effect, patient's request, not visiting, others, multiple reasons, unknown, and not described
Sex	male, female, unknown, not described
Pregnancy/lactation	Without pregnancy/lactation, during pregnancy, during lactation, unknown, not described
Race	Japanese, other Asians, others, unknown, not described
Age (years)	Younger than 15 years, 15 years or older and younger than 65 years, 65 years or older, unknown/not described
Body weight (kg)	Lower than 30, 30 or higher and lower than 40, 40 or higher and lower than 50m, 50 or higher and lower than 60, 60 or higher, unknown/not described
Body height (cm)	Lower than 140, 140 or higher and lower than 150, 150 or higher and lower than 160, 160 or higher and lower than 170, 170 or higher and lower than 180, 180 or higher and lower than 190, 190 or higher, unknown/not described

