### 12.3. Time of evaluation of level of overall improvement

At the final follow-up: The evaluation at the last follow-up in which level of improvement for each patient was assessed as “1. significant improvement”, “2. improvement”, or “3. ineffective” is employed.

Patients who discontinued the administration of this drug should be followed-up until 14 days after the last date of the final administration of this drug, and within this period, the evaluation at the last follow-up in which level of improvement was assessed as “1. significant improvement”, “2. improvement”, or “3. ineffective” is employed.

In patients in whom follow-up was continued, the evaluation for following period should be included in analysis: Time Allowance at evaluation when the start date of the initial administration of this drug is defined as 1 is as follows:

Time of evaluation	Time Allowance(Day)
The last follow-up (patients who were continuously followed up)	

Patients who were followed up for 52 weeks: the start date of the initial administration of this drug + 37 (52 weeks + 14 days)

Time of evaluation	Time Allowance(Day)
	
 
Patients who were followed up for 104 weeks: the start date of the initial administration of this drug + 756 (104 weeks + 28 days)
 
Patients who were followed up for 156 weeks: the start date of the initial administration of this drug + 1120 (156 weeks + 28 days)
 

12.4. Time of evaluation of rate of clinical improvement, rate of complete remission, and level of improvement in endoscopy findings

Time Allowance at evaluation when the start date of the initial administration of this drug is defined as 1 is as follows:

Time of evaluation	Time Allowance(Day)
Within 24 weeks after the administration start	1-168
At least 24 weeks and within 52 weeks after the administration start	169-364
At least 52 weeks and within 76 weeks after the administration start	365-532
At least 76 weeks and within 104 weeks after the administration start	533-728
At least 104 weeks and within 128 weeks after the administration start	729-896
At least 128 weeks and within 160 weeks after the administration start	897-1121

Data of rate of clinical improvement and complete remission with evaluation of endoscopy findings obtained within Time allowance and evaluation of gastrointestinal symptoms within 4 weeks before and after the date of endoscopy implementation should be employed.

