**“2.19.1 Treatment for patients who showed insufficient response to treatment”**

Patients included in analysis: In patients included in safety analysis, patients who discontinued the survey because of “insufficient effect” or patients in whom dose or the number of administration was adjusted because of “insufficient effect” should be

included.

Objective of analysis: Presence or absence of drugs used after discontinuation of this drug and distribution of the drugs used after discontinuation of this drug are shown.

Analysis items: The number of patients included in analysis should be calculated.

The number of patients and rate of these patients by “drugs used after discontinuation of this drug” and ”detailed classifications of drug used after the discontinuation of this drug“ defined in “11 method of dividing hierarchy for data” should be calculated.

Date of patients in whom dose or the number of administration was adjusted because of “insufficient effect” should be obtained from “[HUMIRA BD] converted data for provision for analysis”.

Notes: Detailed classifications of drug used after the discontinuation of this drug may be overlapped.

“2.19.2 Dosage and administration for patients who showed insufficient response to treatment”

Patients included in analysis: In patients included in safety analysis, patients who discontinued the survey because of “insufficient effect” or patients in whom dose or the number of administration was adjusted because of “insufficient effect” should be included.

Objective of analysis: Distribution of dosage and administration for patients who showed insufficient response to treatment is shown.

Analysis items: The number of patients included in analysis should be calculated.

The number of patients and rate of these patients to those included in analysis should be calculated by presence or absence of discontinuation and classification of dosage and administration (patients discontinued by the initial or second administration, patients who received this drug 3 times or more, the maximum dose for the third or subsequent administration is 40 mg/2 weeks, 40 mg/1 week, 80 mg/2 weeks, 80 mg/1 week, 160 mg/2 weeks, 160 mg/1 week, and others). Items with the number of 0, output by items should not be made.

Date of patients in whom dose or the number of administration was adjusted because of “insufficient effect” should be obtained from “[HUMIRA BD] converted data for provision for analysis”.

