### 13.3. Efficacy

“3.1 Level of overall improvement”

Patients included in analysis: Patients included in efficacy analysis

Objective of analysis: Level of overall improvement at the last follow-up is shown.

Analysis items: The number of patients included in analysis should be calculated.

The patients who achieved overall improvement and rate of these patients to those included in analysis based on the level of overall improvement calculated at last follow-up according to “12.3 Time of evaluation of level of overall improvement should be calculated by “The level of overall improvement” and “detailed classification of overall improvement at the level of improved or higher” defined in “11 method of dividing hierarchy of data”.

“3.1.1 Level of clinical improvement (level of improvement in endoscopy findings is “2. shrinkage” or lower and comprehensive evaluation of gastrointestinal symptoms is “1” or lower”

Patients included in analysis: Patients included in efficacy analysis

Objective of analysis: Level of clinical improvement is shown by time of evaluation.

Analysis items: The number of patients included in analysis, the number of patients who achieved clinical improvement and rate of these patients to those included in analysis should be calculated by the time of evaluation.

Notes: The number of patients should be that of patients with data of evaluation of endoscopy findings within relevant period subject to analysis and evaluation of gastrointestinal symptoms in 4 weeks before and after the date of implementation of endoscopy. Time Allowance for the time of evaluation should be according to “12.4. Rate of patients who achieved clinical improvement, rate of patients who achieved complete remission, and time of evaluation of level of improvement in endoscopy findings”.

“3.1.2 Rate of patients who achieved complete remission (level of improvement in endoscopy findings is “1. remission or scar” and comprehensive evaluation of gastrointestinal symptoms is “0” or lower”.

Patients included in analysis: Patients included in efficacy analysis

Objective of analysis: Level of complete remission is shown by time of evaluation.

Analysis items: The number of patients included in analysis, the number of patients who achieved complete remission and rate of these patients to those included in analysis should be calculated by the time of evaluation.

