Objective of analysis: Level of improvement in endoscopy findings is shown by time of evaluation.

Analysis items: The number of patients included in analysis, the number of patients who achieved improvement in endoscopy findings and rate of these patients to those

included in analysis should be calculated by the time of evaluation.

Notes: Time Allowance for the time of evaluation should be according to “12.4. Rate of patients who achieved clinical improvement, rate of patients who achieved complete remission, and time of evaluation of level of improvement in endoscopy findings”. Patients who have evaluation corresponding to Time Allowance of each time of evaluation should be included in analysis.

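### Tables 3.1.1 to 3.3.4 compute each window's rate only among patients with data in it, so later rates are liable to be inflated by uncounted stops for insufficient effect

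*SAP*

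**What the plan says.** Section 12.4 sets six windows for clinical improvement, complete remission and endoscopy findings: days 1-168, 169-364, 365-532, 533-728, 729-896 and 897-1121. For Tables 3.1.1 and 3.1.2, section 13.3 states "The number of patients should be that of patients with data of evaluation of endoscopy findings within relevant period subject to analysis" and also requires a gastrointestinal evaluation within 4 weeks either side of the endoscopy. For Table 3.3.1, and again for the site-specific Tables 3.3.2 to 3.3.4, it states "Patients who have evaluation corresponding to Time Allowance of each time of evaluation should be included in analysis". Tables 3.2.1 and 3.2.2 need a score at the start and another in the window.

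Section 9.1 adds: "When analysis is conducted, missing data at that time is not complemented". Sections 10.3 and 12.4 contain no rule that carries a value forward or counts a patient who stopped as a non-responder.

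The reason for stopping is coded. Section 11 lists: "Occurrence of adverse events, insufficient effect, patient's request, not visiting, others, multiple reasons, unknown, and not described". Section 10.1 treats patients who have not discontinued administration as the ones continuing in the survey. Tables 2.19.1 and 2.19.2 cover "patients who discontinued the survey because of" insufficient effect, but they use the safety set and report later drugs and dosing, not response.

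Two other parts of the plan work differently. Section 9.2 says of unknown and not-described values that such "data should be included in denominator" when rates are calculated. Section 12.3 keeps patients who stopped in the overall-improvement endpoint, through their last assessment up to 14 days after the final dose.

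**The concern.** A patient who stops because the drug did not work is the clearest treatment failure in the survey. Under these rules that patient contributes to a window only if a qualifying evaluation falls in it. A patient who stops at week 20 and is not scoped afterwards is absent from all windows from week 24 on. A rate can then rise with nobody improving. Suppose 100 patients are due and all are scoped, with 48 improved (48%). If 20 of the unimproved leave before the next window and nothing else changes, the table shows 48/80 = 60%.

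Section 3.1 says the results go into the report to the regulator and the reassessment application. Section 4.3 says the earlier trial was open-label with 20 patients, so these tables carry much of the long-term picture.

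The fall in N does not explain itself. Part of it is planned, because section 2 gives patients 52, 104 or 156 weeks of follow-up according to start date. The rest mixes stopping for insufficient effect, stopping for other reasons, and continuing without an endoscopy.

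**Working it through.** **Inputs.** The denominators come from section 13.3, the windows from 12.4, the no-imputation rule from 9.1, the stopping reasons from 11 and the cohorts from 2. The plan gives no expected response rate, stopping rate or endoscopy uptake, and section 4.3 leaves the number of patients undecided. There is no stated figure to reproduce, and every value of r and d below is an assumption.

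**Step 1. Effect of losing the failures.** Let r be the rate among patients with data in a window. Let d be the share of patients due in that window who stopped for insufficient effect before it and have no evaluation in it. Counting them as failures gives

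rate among patients due = r × (1 − d), a difference of r × d.

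This gives all other patients due, with or without data, the rate r.

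| Observed r | d = 5% | d = 10% | d = 20% | d = 30% |
|---|---|---|---|---|
| 40% | 38% | 36% | 32% | 28% |
| 60% | 57% | 54% | 48% | 42% |
| 80% | 76% | 72% | 64% | 56% |

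At r = 60% and d = 40% the result is 0.60 × 0.60 = 36%. Over the tabulated range the difference runs from 0.40 × 0.05 = 2 points to 0.80 × 0.30 = 24 points.

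**Step 2. Effect of who is scoped.** Suppose the true rate in all patients not lost as failures is 60%. The rate among patients due is then 0.60 × (1 − d), while the table shows the rate in those scoped.

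- d = 10%, 60% among those scoped: 60 − 54 = +6 points.
- d = 10%, 50% among those scoped (symptomatic patients scoped more often): 50 − 54 = −4 points.
- d = 20%, 50% among those scoped: 50 − 48 = +2 points.
- d = 20%, 70% among those scoped: 70 − 48 = +22 points.

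Losing the failures always pushes the rate up, but the net error can be small or reversed.

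**Step 3. Why the failures cannot simply be added to the scoped patients.** Take 100 due, 20 stopped for insufficient effect, 80 continuing, and 60% improved among those scoped.

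- All 80 scoped: 48/(80 + 20) = 48%.
- 40 scoped: 24/(40 + 20) = 40%.
- 20 scoped: 12/(20 + 20) = 30%.

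Stopping and response are identical in all three cases and only endoscopy uptake differs. The form r × (1 − d) gives 0.60 × 0.80 = 48% each time.

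**The case against.** An observed-case table with its denominator printed is a recognised descriptive choice in a single-arm, all-case survey. These tables carry no test and no comparator. The endpoint behind Table 3.1 and the tested factor analysis in Table 3.4 is overall improvement at last follow-up, and section 12.3 already keeps patients who stopped in it. All of this stands, and it keeps the point small.

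A reader might infer three stronger things that the plan does not support.

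- *The later rates are inflated.* The plan gives neither the stopping rate nor the endoscopy uptake, and step 2 shows that the net error can reverse.
- *The rates describe only patients still on the drug.* Section 12.4 has no on-treatment restriction, so a patient who stopped counts wherever a qualifying endoscopy exists.
- *The tables hide the attrition.* Each prints its N per window. Table 1.1.1 [2] gives the efficacy set by follow-up period. Table 1.6 gives treatment duration for that set, with class limits at days 168, 364 and 728 that match limits in 12.4. Table 1.7 gives reasons for stopping.

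These other tables do not close the gap. Table 1.6 carries no reasons. Table 1.7 uses the safety set and is not split by window or cohort. No table links the reason for stopping to the patients missing from a given efficacy window.

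**Conclusion.** The point holds in limited form. The denominators in Tables 3.1.1, 3.1.2 and 3.3.1, and by the same rule in 3.3.2 to 3.3.4 and 3.2.1 to 3.2.2, leave out patients who stopped for insufficient effect and have no qualifying evaluation in the window. The later rates are liable to be inflated on that account. For an assumed observed rate of 60% and d of 10% to 40%, the overstatement is 6 to 24 points if those with data represent the other patients due. The actual size and net direction cannot be determined from the plan. Tables 3.1 and 3.4 are not affected in this way. This is an inexpensive improvement to descriptive tables and does not invalidate them.

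**What to change.** Keep the observed-case row in every table. For each window add:

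1. The number due: efficacy-set patients whose cohort's planned follow-up reaches the window. By section 2 the 52-week cohort is due in the first two windows of 12.4, the 104-week cohort in the first four, and the 156-week cohort in all six. In Tables 3.3.2 to 3.3.4 restrict this to patients with that site ticked before the start. In 3.2.1 and 3.2.2, apply the same cohort rule to the 12.5 time points and restrict it to those with a starting score.
2. The number with data.
3. The number stopped before the window, by reason.
4. One sensitivity rate among patients due, r × (1 − d). Patients who stopped for insufficient effect before the window and have no evaluation in it count as not improved or not in remission.

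Do not add everyone who stopped to the scoped patients, because that over-weights failures when endoscopy uptake is incomplete (step 3). If stops for adverse events are also counted as failures, show that as a separately labelled convention, since such a patient may have been in remission. State in advance how multiple, unknown and undescribed reasons are classified.

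The inputs exist: start-date cohort, derived last treatment date, discontinuation status and coded reason. No new data are needed. The downside is a less favourable figure that assumes scoped patients represent those due but not scoped, including those who stopped for other reasons. The sensitivity rate leaves the first window unchanged, because nobody has stopped before day 1.

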## 8. Definition of population used for analysis

Name of population	Definition
Patients who were transferred to another institutions	Patients registered at different institutions in duplicate are applicable.
Registered patients	Patients who are eligible for registration based on registration assessment are applicable.
Not registered patients	Patients not registered for whom survey sheet data was collected are applicable.
Patients for whom a survey sheet data was fixed	Patients for whom a survey sheet data was fixed are applicable.
Patients for whom a survey sheet data was not fixed	Patients for whom a survey sheet data was not fixed are applicable. As a reason for unfixed survey sheet, “patients for which survey sheet cannot be collected” should be chosen for applicable patients extracted from “[HUMIRA BD] Patients whose survey

Name of population	Definition
	sheet cannot be collected.xls”
Patients excluded from safety analysis	
Patients corresponding to exclusion conditions for safety analysis are applicable. For exclusion conditions for safety analysis, standard data “Adoption or not adoption of patients” should be referred to.
 
Items of exclusion are as follows:
 
 
• Violation of contract: Institutions/departments with which contract is not concluded
 
• Physicians outside the contract
 
• Period excluded from survey period
 
• Patients who have not received this drug
 
• Patients without physician’s evaluation
 
• Duplicated patients
 
• Patients who were transferred to another institutions
 
• Patients in whom safety cannot be assessed
 
• Patients who received this drug before the contract
 

Patients included in safety analysis	Patients included in those for whom survey sheet was fixed after excluding those excluded from safety analysis
Patients excluded from efficacy analysis	
Patients corresponding to exclusion conditions for efficacy analysis are applicable. For exclusion conditions for efficacy analysis, standard data “Adoption or not adoption of patients” should be referred to.
 
Items of exclusion are as follows:
 
 
• Patients with diseases which is not subject to the survey
 
• Patients in whom efficacy cannot be assessed
 

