### 10.3. Efficacy analysis

Name of data	Derivation and calculation method
Level of overall improvement	Description of level of overall improvement in the survey sheet (assessment provided by attending physician) should be employed.
Clinical improvement	Patients with the level of improvement in endoscopy findings in the survey sheet of “2. shrinkage” or lower and comprehensive evaluation of gastrointestinal symptoms in the survey sheet of “1” or lower (0, 1) are assessed as patients with clinical improvement.
Complete remission	Patients with the level of improvement in endoscopy findings in the survey sheet of “1. remission or scar” and comprehensive evaluation of gastrointestinal symptoms in the survey sheet of “0” are assessed as patients with complete remission.
Improvement in gastrointestinal symptoms (abdominal pain, diarrhoea, other gastrointestinal symptoms)	If comprehensive evaluation of gastrointestinal symptoms or evaluation of each gastrointestinal symptom differs by 1 point or higher compared to those at the start of the administration of this drug (points of evaluation at the start of administration - those at each evaluation $\geq$ 1), patients are assessed as those who obtained improvement.

Name of data	Derivation and calculation method
Level of improvement in endoscopy findings	Description in “level of improvement in ulcer with the maximum diameter” in the level of endoscopy findings in the survey sheet should be employed.
Main symptoms and accessory symptoms of Behcet disease	Description in evaluations for each main and accessory symptom in efficacy evaluation in the survey sheet should be employed. “0” should be defined as “no symptom”, “1,2,3” should be defined as “there are any symptoms”, unknown or not described data should be defined as “unknown/not described”
CRP	Measurement in the survey sheet should be employed. If measurement is undetectable, the measurement should be deemed as undetectable limit.

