Detailed classifications of medical history	tuberculosis, bacterial bronchitis, nontuberculous mycobacterial infection, aplastic anaemia, pancytopenia, malignant tumour, others
Previously used drug/previous treatment	Absent, present, unknown, not described
Classification of biological preparation as previously used drug/previous treatment	Adalimumab, infliximab, others
Classification of drugs other than biological preparation as previously used drug/previous treatment	Biological preparation, aminosalicylic acid preparation, steroid, immunomodulative drug, antibiotic, other previously used drug, operation, other previous treatment
Concomitant drug	Absent, present, unknown, not described
Detailed classification of concomitant drugs	Aminosalicylic acid preparation, oral adrenocortical steroid, immunomodulative drug, immunosuppressive drug, enteral nutrient, colchicine, others
Combination therapy	Absent, present, unknown, not described
Detailed classification of combination therapy	Operation, others
Endoscopy	Absent, present, unknown, not described

data	Method of dividing hierarchy
Detailed classifications of endoscopy	Ileocecum, colon, esophagus, others
Level of improvement in endoscopy findings	Remission or scar, shrinkage, no change, aggravation, not assessed
Evaluation of gastrointestinal symptoms	
0,1,2,3,4
 
0: No symptom
 
1: There was symptom in last 2 weeks but daily living activities were rarely disturbed.
 
2: There was symptom in last 2 weeks and daily living activities were slightly disturbed.
 
3: There was symptom in last 2 weeks and daily living activities were disturbed.
 
4: There was symptom in last 2 weeks and daily living activities were severely disturbed.

Detailed classifications of gastrointestinal symptoms	Abdominal pain, diarrhoea, others (including bloating, abdominal tenderness, haemorrhage)
Self-administration	Absent, present
Self-administration error	Absent, present, unknown, not described
Drug used after the discontinuation of this drug	Absent, present, unknown, not described
Detailed classifications of drug used after the discontinuation of this drug	Aminosalicylic acid preparation, steroid, immunomodulative drug, biological preparation, other drug
Level of overall improvement	Significant improvement, improvement, ineffective
Detailed classifications of level of overall improvement for patients with improvement or higher level of improvement	Significant improvement, improvement

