Notes: The number of patients should be that of patients with data of evaluation of endoscopy findings within relevant period subject to analysis and evaluation of gastrointestinal symptoms in 4 weeks before and after the date of implementation of endoscopy. Time Allowance for the time of evaluation should be according to “12.4. Rate of patients who achieved clinical improvement, rate of patients who achieved complete remission, and time of evaluation of level of improvement in endoscopy

findings”.

“3.2.1 Comprehensive evaluation of gastrointestinal symptoms at each time of evaluation”

Patients included in analysis: Patients included in efficacy analysis

Objective of analysis: Comprehensive evaluation of gastrointestinal symptoms is shown by time of evaluation.

Analysis items: The number of patients included in analysis, the number of patients have comprehensive evaluation of gastrointestinal symptoms (0,1,2,3,4) and rate of these patients to those included in analysis, the number of patients who achieved improvement in gastrointestinal symptoms and rate of these patients to those included in analysis should be calculated by time of evaluation.

Notes: Time Allowance at time of evaluation should be according to “12.5 Time of evaluation of gastrointestinal symptoms”. Only patients who have evaluation corresponding to administration start and Time Allowance of each time of evaluation should be included in analysis.

“3.2.2 Evaluation of gastrointestinal symptoms at each time of evaluation”

Patients included in analysis: Patients included in efficacy analysis

Objective of analysis: Evaluation of gastrointestinal symptoms is shown by time of evaluation.

Analysis items: The number of patients included in analysis, the number of patients who have evaluation of gastrointestinal symptoms (0,1,2,3,4) and rate of these patients to those included in analysis, the number of patients who achieved improvement in detailed classifications of gastrointestinal symptoms and rate of these patients to those included in analysis should be calculated by time of evaluation.

Notes: Time Allowance at time of evaluation should be according to “12.5 Time of evaluation of gastrointestinal symptoms”. Only patients who have evaluation corresponding to administration start and Time Allowance of each time of evaluation should be included in analysis.

“3.3.1 Level of improvement in endoscopy findings”

Patients included in analysis: Patients included in efficacy analysis

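### The symptom improvement rates in Tables 3.2.1 and 3.2.2 keep patients with a start score of 0, who cannot improve, in the denominator; this matters mainly for the single symptoms in Table 3.2.2

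*SAP*

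**What the plan says.** SAP section 10.3 defines improvement in gastrointestinal symptoms. The score must be one that "differs by 1 point or higher compared to those at the start of the administration of this drug", and the direction is fixed by the formula in brackets ("points of evaluation at the start of administration - those at each evaluation"), which must be at least 1. The rule covers the overall score and the single symptoms alike: "If comprehensive evaluation of gastrointestinal symptoms or evaluation of each gastrointestinal symptom".

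Section 11 sets the scale at 0 to 4, with 0 meaning no symptom. It lists the single symptoms as "Abdominal pain, diarrhoea, others (including bloating, abdominal tenderness, haemorrhage").

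Section 13.3 then sets the rates. Table 3.2.1 reports "the number of patients who achieved improvement in gastrointestinal symptoms and rate of these patients to those included in analysis". Table 3.2.2 reports "the number of patients who achieved improvement in detailed classifications of gastrointestinal symptoms and rate of these patients to those included in analysis". The notes to both tables define who is included: "Only patients who have evaluation corresponding to administration start and Time Allowance of each time of evaluation should be included in analysis". The condition is that both evaluations exist. It does not concern the value of the first one.

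The efficacy exclusions in section 8 work at patient level. They cover patients whose disease is outside the survey and "Patients in whom efficacy cannot be assessed". Neither refers to a start score.

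**The concern.** A patient who scores 0 for an item at the start has no room to fall, yet is counted at every later visit as someone who did not improve. The printed rate therefore depends on two things: how often symptomatic patients improved, and how many patients had the symptom to begin with. A reader cannot separate the two from the rate alone.

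This bears most on Table 3.2.2. Abdominal pain, diarrhoea and the residual group are each scored separately, and nothing in the survey's entry condition (section 4.2) requires a patient to have all of them. If the symptoms differ in how common they are at the start, their improvement rates stand on different footings, and a low rate may only mean that few patients had the symptom.

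These symptom evaluations are among the efficacy items listed in section 5.1, and section 3.1 says that results may go into the reassessment application, so the figures are likely to be read and quoted.

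**Working it through.** The SAP states no rate or sample size for these tables, so there is no planned figure to reproduce. The check has two steps.

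**Step 1: who can meet the rule.** Inputs are the scale (section 11) and the threshold (section 10.3). The largest possible fall equals the start score:

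| Start score | Largest possible fall | Can count as improved? |
|---|---|---|
| 0 | 0 | No |
| 1 | 1 | Yes |
| 2 | 2 | Yes |
| 3 | 3 | Yes |
| 4 | 4 | Yes |

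Only a start score of 0 rules improvement out.

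**Step 2: effect on the rate.** For one item at one visit, let N be the patients with both evaluations, N0 those among them who started at 0, and x the number improved. All x come from the N − N0 patients who started at 1 or more. Write f = N0/N and r = x/(N − N0). Then

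reported rate = x/N = [x/(N − N0)] × [(N − N0)/N] = r × (1 − f).

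The highest rate that the table can show is 1 − f, reached when every symptomatic patient improves.

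The SAP gives neither f nor r, so every value below is an assumption:

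| Assumed r | f = 10% | f = 30% | f = 50% |
|---|---|---|---|
| 50% | 45% | 35% | 25% |
| 60% | 54% | 42% | 30% |
| 70% | 63% | 49% | 35% |
| 90% | 81% | 63% | 45% |

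For example, 0.60 × 0.90 = 0.54, 0.60 × 0.70 = 0.42 and 0.60 × 0.50 = 0.30.

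**What this does to comparisons between symptoms.** Two symptoms with the same 60% rate among affected patients would print as 54% and 30% if 10% and 50% of patients lacked them at the start. The order can also reverse. A symptom with r = 70% and f = 50% prints as 35%, below a symptom with r = 50% and f = 10%, which prints as 45%.

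**The case against.** The strongest reply is that the share of all evaluable patients whose score fell is an openly defined quantity, and that the information needed to read it is largely there. Both tables print the 0 to 4 distribution by time of evaluation, and section 12.5 includes administration start among those times. The number starting at 0 is therefore visible for each item, and the numerator would not change under a restricted denominator. What remains is a real gap. The start-0 count is not shown for the patients evaluable at each later visit, and a later score of 0 merges patients whose symptom resolved with those who never had it. The restricted rate can be approximated where nearly everyone is evaluable, but not recovered in general.

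Four further points stand and limit the weight of the finding:

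- Section 4.2 takes only patients who did not respond to existing treatment, so a comprehensive score of 0 at the start is plausibly uncommon. Dilution in Table 3.2.1 is probably small.
- No test, interval or success criterion is attached to these tables. Table 3.4 uses the physician's overall improvement. Clinical improvement and complete remission (section 10.3) use the score at the visit, not the change. None of these is affected.
- The restricted rate is never lower than the present one, and it leaves out patients who can only stay the same or worsen. It should not be reported without showing what happened to them.
- Tables 3.3.2 to 3.3.4 do restrict on a baseline finding, but there the ulcer site defines which subgroup the table describes. They are weak support for a rule about patients unable to improve.

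A reader might go further and infer that the rule distorts a treatment effect. The document does not support this: these tables have no comparator, and neither denominator estimates such an effect. A reader might also blame this rule for all loss of comparability between visits. That too goes too far. The evaluable group changes because both evaluations are required, patients stop, and planned follow-up is 52, 104 or 156 weeks depending on start date (section 2). Restricting the denominator removes variation in the start-0 share but not the rest.

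**Conclusion.** The point holds as a flaw in how a descriptive rate is defined. Under sections 10.3, 11 and 13.3 taken together, every patient with a start score of 0 lowers the reported improvement rate and cannot raise it, and nothing in section 4.2 or section 8 removes such patients. The relation, reported rate = r × (1 − f), is exact.

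The size is not known. The 54%, 42% and 30% figures rest on an assumed 60% rate and assumed shares of 10%, 30% and 50%; the SAP gives no baseline symptom distribution. That Table 3.2.2 is the main problem and Table 3.2.1 a small one is a judgement from the entry condition and the separate scoring of symptoms, not a figure in the plan. The correction is worth making because it is cheap and changes a reported efficacy figure. No inferential result depends on it.

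**What to change.** Add one sentence to section 10.3 and to the notes of Tables 3.2.1 and 3.2.2: for each item, the improvement rate is computed among patients with a start score of 1 or more who also have an evaluation in the visit window, and that denominator is printed at each visit. Keep the 0 to 4 distribution for all patients with both evaluations. Add a row for patients who started at 0, giving the number who stayed at 0 and the number who rose to 1 or more, so that the restriction does not hide worsening.

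The cost is a smaller denominator for the improvement row, and so a less precise rate, plus one extra row per item. No new data are needed.
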